To demonstrate the feasibility and impact of shared care on patient experiences and outcome, waiting times and the capacity to better handle the mental health problems at an early stage within primary care. Shared care means a Norwegian adjusted model of the Family Health Team model developed in Hamilton, Canada, where GPs, clinicians and other professionals from primary care and specialized mental health care working together as a team co-located in primary care. The adjusted model of shared care will be tested against current practice in a cluster randomized trial.

Work packages (WPs)

WP1 will investigate current practice and areas for improvement of services and collaboration, based on data extracted from the electronic registers in the collaborating services and on survey data from patients and health care workers.

WP2 will be done by the collaborating services supported by the research group. The Family Health Team model of shared care will be adjusted to the Norwegian context, based on results of WP1 and a study visit to Canada. Then the adjusted model will be implemented, and the implementation process and facilitators and barriers for implementation will be investigated.

WP3 will compare implemented shared care to current practice regarding access to services, distribution of patients, patient experiences and outcome, and distribution of tasks and competences. We will use a difference-in-difference model with randomised clustering of GPs regarding shared care or current practice.

The research group has received financial support from the Regional Health Authority in South-Eastern Norway to initiate this research on shared care, and this money will cover WP2 and parts of WP1. (See attached pdf-file with budget). This application is for a PhD research fellow for WP1 and a postdoc research fellow for WP3, and some support for data collection in WP3.

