During 2013 there have been discussions between the CMHC and the boroughs on how to improve the collaboration between the primary care and the specialized mental health care, and the services are finding that the model of shared care may be adjusted to the local context. Some GPs have also been involved in these discussions, and the GPs in the research group will approach the GP groups in the boroughs during this winter with specific invitation to six GP groups (two in each borough) with altogether approximately 24 GPs to participate in the project.

Cohort definitions and methods common for WP1 and WP 3

In WP1 and WP3 we will collect data from two similar cohorts of patients and in similar ways. This is outlined here and referred to in the descriptions of WP1 and WP3 below.

We will recruit approximately 24 GPs working in two different GP group practices in each of the three boroughs listed above. These GPs must be willing to take part in both WP1 and WP3, and they must be willing to be randomized (as groups) to be involved in shared care or continue with current practice.

Register Cohort

Register Cohort: All patients 16-65 years old and seen by the 24 GPs during 12 months. The reason for choosing 12 months is to have a long enough period to get enough data on referrals between services.

Variables: Age, gender, marital status, borough, GP, referrals, ICPC-2 codes/ICD-10 diagnoses, GAC scores, GP consultations, outpatient consultations and inpatient stays in specialized mental

health and substance abuse services, type of ward/team, use of coercion, codes on treatment procedures, social care, employment, sick leave and prescriptions of medication.

Data collection: Data are extracted from the GP patient records, accident and emergency clinics in Oslo, Akershus University Hospital (specialized mental health and substance abuse services for adults and youth), NAV (the social care, work/sick leave and social security agency). Data

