Estimated size of the Clinical Cohort: Building on the estimated size of the Register Cohort (above), we estimate that the 24 GPs will see altogether 1800 patients during 4 weeks, as 4 weeks are 1/11 of the 44 weeks a year that the GP is required to run their practice. If 75 % give consent to take part in the study on patient satisfaction and outcome, this will be 1350 patients.

Estimated size of the Health Worker Cohort: Approximately 24 GPs, 40 clinicians at outpatient clinics and mobile teams and 60 mental health and social workers in the boroughs is expected to fill in the questionnaire on experiences of current practice, needs for improvements and shared care.

Handling of completed questionnaires and data files

Completed questionnaires from the Clinical Cohort will be kept locked in a safe place at each GP group and collected weekly by the PhD candidate or other members of the research group. The data will be registered by project coordinators in the R&D Department in the Division of Mental Health Services, Akershus University Hospital, in a data base on the approved and secure research server dedicated to research data in Akershus University Hospital. The anonymous data files from the Register Cohort will also be saved on the same dedicated research server at the hospital.

Approval of the project

Application is sent in February 2014 to the Regional Committee on Ethics in Health Research (REK) for approval of the project, including extracting data from the electronic registers and for having the data linked by NAV. The data file that will be made available for the research group will be anonymous.

WP1: Study of current practice and needs for improved collaboration

The aim for WP1 is to study current practice and study needs for improved collaboration. These results will also be used as a baseline in the before-and-after design to control for differences among sites in the comparative study in WP3.

Research questions for WP1

1. What are the characteristics of patients seen in the current practice (ICPC-2 codes, mental health problems, drug problems, functioning, service utilization, quality of life)?
2. What are the patterns of collaborative contacts and activities?
3. How satisfied are patients with the services they receive and the collaboration between them?
4. What do the GPs, primary care and mental health services want and need regarding collaboration and competence?

Design of WP1

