See above for descriptions common to WP1 and WP3, as well as definitions of the cohorts.

Cohorts and periods for data collections in WP1

Register Cohort in WP1 will be all patients seen by the 24 GPs from July 1st 2013 to June 30th 2014. The data will be extracted from the registers for the same period of time. The data extraction will be done in September 2014. Clinical Cohort in WP1 will be patients seen by the 24 GPs during four weeks in May/June 2014. Health Worker Cohort in WP1 will be the 24 GPs and the clinicians and health workers in the other agencies in May 2014.

WP2: Adapting and implementing the Norwegian model for shared care

WP2 will be done by the collaborating services supported by the research group. The Family Health Team model of shared care will be adapted to the Norwegian context, based on results of WP1 and a visit to Canada to learn more about the model. In this process we follow advice given by the Medical

Research Council in UK regarding the needs to adapt models to the local context as a part of research (Craig et al 2008). Then the Norwegian model will be implemented, and the implementation process and facilitators and barriers for implementation will be investigated.

A suggested outline of the framework for a model for shared care

Following discussions in the research group and with some of the services interested in trying a model of shared care, a suggested framework for a model may be: Shared care is implemented by developing a multidisciplinary team of health and social workers from the primary mental health care, the outpatient clinic of the CMHC and social care (NAV). There should be rooms available for the team within or close to the GP groups taking part in shared care.

There may be one team serving all the three GP groups, or there may be separate teams or sub- teams. If there are separate teams, some of the resources may be shared by the teams.

The teams may include persons full time or part time, and it may have access on a regular or ad hoc basis to persons working in other services not represented in the team.

The process of defining and deciding on design of the adjusted shared care model

The Norwegian shared care model will be specified late in the autumn of 2014 based on the following sources of information:

- Analyses of the patterns of distribution and referrals between the GPs, primary mental health care, social care and specialised mental health services.

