5. Is co-morbidity (somatic, substance abuse) better identified and treated with the Norwegian shared care model than in current practice?
6. Are there competences in service providers that promote closer collaboration?
7. Are GPs and other services more satisfied with the Norwegian shared care model than with their earlier practice?
8. What is the patient course and outcome with the Norwegian shared care model compared to current practice?
9. What is the impact on the patient experience?
10. Also increase in collaboration between GPs and primary health care?

Design of WP3

See above for descriptions common to WP1 and WP3, as well as definitions of the cohorts.

Cohorts in WP3

The Register Cohort in WP3 will be all patients seen by the 24 recruited GPs (see above) from January 1st 2016 to December 31st 2016. The data will be extracted from the registers for the same period of time. This is the year after the implementation during 2015 of the adjusted model of shared care. The data extraction will be done in February 2017. The Clinical Cohort in WP3 will be patients seen by the 24 GPs during four weeks in January 2016. The Health Worker Cohort in WP3 will be the 24 GPs and the clinicians and health workers in the other agencies in January 2016.

Cluster randomized controlled trial

WP3 is a cluster randomised study. Two GP groups in each of the three boroughs will be randomised to take part in the implementation of shared care or continue with their current practice. The randomisation will be done in the summer of 2014, so that some GPs randomised to shared care may take part in the planned study visit to Canada in September 2014 to see the Family Health Team model in operation. The GPs randomised to current practice may take part in implementing shared care after the research study if the model proves to be successful.

Power calculations for the Clinical Cohort in WP3

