Power calculation with 90 % power and CSQ as primary outcome measure shows that to detect a difference of half a SD (3.8) in patient satisfaction between shared care and current practice, we need 85 patients in each arm in a controlled trial with randomisation of individuals. For a cluster randomised trial with ICC=0.03 and 12 GPs in each arm, we need 101 patients in each arm (9 or more per GP). Calculation is done as defined for cluster randomised trials in health services research (Eldridge & Kerry 2012), with elaboration of the CONSORT statement in relation to cluster randomised trials (Schultz et al 2010, Moher et al 2010).

Statistical analyses

Standard statistical analyses will be used to describe various parts of the material, test significant differences, and analyse explanatory models. Growth curve or multilevel analyses will be done of individual progress, with data on the use and services (including collaboration) as explanatory variables. Statisticians at the Research Centre, Akershus University Hospital will give advice and assist with more complex analyses, such as growth curve analysis.

The project plan, project management, organization and cooperation

Principal Investigator is [name], head of the The R&D Department, Division Mental Health Services, Akershus University Hospital (Ahus). The department has 7 senior researchers (3 psychiatrists, 1 child/adolescent psychiatrist, 3 psychologists). One is professor and two are associate professors at the University of Oslo. There are 12 PhD research fellows and a research support staff. Implementation and quality of mental health services is one priority area, and experiences of users and carers another. The department is co-located with the Health Services Research Centre, with statisticians and ICT experts on patient data extraction.

Project group (see also CVs)

[name], Principal Investigator. Head of R&D Department Mental Health Services, Akershus University Hospital (Ahus), specialist in psychiatry and professor at the Clinic for Health

Services Research and Psychiatry, Institute of Clinical Medicine, University of Oslo. He has been medical director and psychiatrist at a pioneering CMHC with close collaboration with primary care, and he has extensive experiences in mental health services research.

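### The power calculation counts 12 GPs per arm as clusters, but GP groups are randomised, three per arm, so 101 patients per arm does not give 90 % power.

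*Protocol*

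**What the plan says.** The unit of randomisation is the GP group. Under the cohort definitions common to WP1 and WP3, the GPs are told that "they must be willing to be randomized (as groups) to be involved in shared care or continue with current practice". The setting section plans a "specific invitation to six GP groups (two in each borough) with altogether approximately 24 GPs to participate in the project". The WP3 section on the cluster randomised trial says "Two GP groups in each of the three boroughs will be randomised to take part in the implementation of shared care or continue" with current practice. The outline of the shared care model agrees with three groups in the intervention arm: "There may be one team serving all the three GP groups".

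The section on power calculations for the Clinical Cohort in WP3 uses another unit. It starts from 85 patients per arm under individual randomisation, for 90 % power to detect half an SD (3.8 points) on the CSQ-8, the primary outcome. It then states: "For a cluster randomised trial with ICC=0.03 and 12 GPs in each arm, we need 101 patients in each arm", that is, nine or more per GP. It does not say whether the ICC of 0.03 describes patients of one GP or of one GP group. Nowhere does the Protocol randomise individual GPs or explain why the GP serves as the cluster.

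The number of patients expected is much larger than 101 per arm: "If 75 % give consent to take part in the study on patient satisfaction and outcome, this will be 1350 patients". The WP1 results are to be "used as a baseline in the before-and-after design to control for differences among sites", and the work-package summary speaks of a "difference-in-difference model with randomised clustering of GPs".

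**The concern.** In a cluster randomised trial the design effect depends on how many units are randomised and how many patients each contains. Entering 12 clusters per arm where there are three makes each cluster look a quarter of its real size and understates the inflation. It also hides that, with six randomised units, the number of groups limits precision more than the number of patients does.

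This is the only sample-size justification given for the primary outcome. If recruitment or follow-up fell towards the stated target, the trial could be described as 90 % powered when it is not. At the expected size, whether 90 % is reached depends on three things that the calculation does not state: the GP-group ICC, the degrees of freedom, and the gain from the baseline period.

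**Working it through.** **Inputs from the Protocol.** Difference 0.5 SD; power 90 %; 85 per arm before clustering; ICC 0.03; 12 GPs per arm; six GP groups, so k = 3 per arm; 1350 expected patients, so 675 per arm. Alpha is not stated. I assume 5 % two-sided, because 2 × (1.960 + 1.282)² / 0.5² = 84.1, which rounds up to the Protocol's 85.

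**Reproducing 101.** With 12 clusters per arm, cluster size is 85/12 = 7.08 and the design effect is 1 + 6.08 × 0.03 = 1.1825. Then 85 × 1.1825 = 100.5, rounded up to 101. The formula is used correctly; the cluster count is what conflicts with the design.

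**The same 101 with three groups per arm, ICC 0.03 for the group.**
- Patients per group: m = 101/3 = 33.7.
- Design effect: 1 + 32.67 × 0.03 = 1.98.
- Effective size: 101/1.98 = 51 per arm.
- Noncentrality: 0.5 × √(51/2) = 2.53.
- Power: 71 % by normal approximation; 48 % on a t-test of six group means (4 df).

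**Size needed.** By normal approximation, n = 85 × (1 − 0.03) / (1 − 85 × 0.03/3) = 82.45/0.15 = 550 per arm. On 4 df without baseline adjustment, power at ICC 0.03 levels off at about 75 % however many patients are added.

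**Unadjusted power for 0.5 SD, three groups per arm.** The variance of a group mean is ICC + (1 − ICC)/m in SD² units, and the standard error of the difference is √(2 × variance/3). The ICC range is an assumption.

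| GP-group ICC | 101 per arm: normal / 4 df | 675 per arm: normal / 4 df |
|---|---|---|
| 0 | 94 % / 76 % | above 99 % / above 99 % |
| 0.005 | 91 % / 70 % | above 99 % / above 99 % |
| 0.01 | 87 % / 64 % | above 99 % / 96 % |
| 0.03 | 71 % / 48 % | 91 % / 70 % |
| 0.05 | 59 % / 39 % | 75 % / 52 % |

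At 675 per arm, 90 % on 4 df needs a group ICC of about 0.015 or less. With an assumed 40 % loss (405 per arm) and ICC 0.03, power is 89 % / 67 %.

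**With the baseline period.** For a difference-in-difference on group means with different patients in each period, the variance of a group's change is 2 × ICC × (1 − r) + (1 − ICC)(1/m₁ + 1/m₂). Here r is the between-period correlation of the group effects, and m₁ and m₂ are the patients per group in the two periods. The Protocol gives no r; 0.5 to 0.9 is assumed, with ICC 0.03.

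| Patients per arm (baseline / WP3) | Normal, r = 0.5 to 0.9 | 4 df, r = 0.5 to 0.9 |
|---|---|---|
| 101 / 101 | 54 % to 68 % | 36 % to 46 % |
| 675 / 101 | 68 % to 87 % | 46 % to 65 % |
| 675 / 675 | 88 % to above 99 % | 65 % to 96 % |

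**The case against.** The strongest objection is that the Protocol does not plan to stop at 101 per arm. It expects about 675, and by the normal approximation that reproduces its own 85 and 101, three groups per arm at ICC 0.03 then give 91 %. On that method the planned trial roughly meets its aim after the cluster count is corrected. This stands, and it limits the practical harm. It does not make the stated requirement of 101 right, and the normal approximation is optimistic with six randomised units.

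Second, because 0.03 is paired with 12 GPs, it may be a within-GP correlation, and the group-level part could be smaller. Suppose a total of 0.03 is split between GP and group, with four GPs per group and an assumed group-level part of 0 to 0.015. Then 101 per arm gives 90 % down to 80 % by normal approximation and 68 % down to 57 % on 4 df. At 675 the 4-df figures are 98 % down to 85 %. So 101 holds up only if there is no group-level correlation at all and the small number of clusters is ignored.

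Third, the 4 df belong to an unadjusted comparison of group means, which the Protocol does not prescribe; the analysis method may properly be set in an SAP. That is fair, and it is why both sets of figures are shown. At ICC 0.03 for the group, 101 falls well short on either.

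Fourth, the WP1 baseline could be full-size even if WP3 recruited only 101 per arm. The table includes that case, and it still stays below 90 %.

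**Conclusion.** The concern holds. The randomised unit is the GP group, three per arm, and the sample-size calculation uses 12 GPs per arm. At ICC 0.03 for the group and 5 % two-sided, the stated 101 per arm gives 71 % power by normal approximation or 48 % on 4 df, against the 90 % claimed. On 4 df without baseline adjustment it falls short even with no clustering (76 %). By normal approximation it reaches 90 % only if the group ICC is about 0.005 or less.

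The expected cohort is a separate matter. At 675 per arm, power lies between clearly adequate and clearly inadequate depending on the group ICC, the degrees of freedom and the between-period correlation. The Protocol does not settle any of these, so it does not show 90 % power at that size either.

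**What to change.** Rewrite the power paragraph:

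- Take the GP group as the cluster, three per arm.
- State alpha and the level to which the ICC refers, with a range for the GP-group ICC.
- Use small-cluster degrees of freedom.
- Replace the target of 101 with the power or detectable difference for the expected 1350 patients, allowing for loss to follow-up. Unadjusted on 4 df at 675 per arm, for example, power for 0.5 SD is 96 %, 70 % and 52 % at ICC 0.01, 0.03 and 0.05. The differences detectable with 90 % power are 0.43, 0.66 and 0.84 SD.
- If credit is taken for the difference-in-difference baseline, state the assumed between-period correlation.

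As a clarification only, one line in the WP3 analysis text could say that inference is at GP-group level with a small-sample correction, with GP nested below if wanted.

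The cost is one rewritten paragraph and one added line. The stated power will look less favourable, but no patients beyond the expected 1350 are needed and the design does not change.

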The results will be given as feedback to the various services, including a profile of their practice and the average profile for similar services in the project. Three scientific papers from each of the research fellows will be published, as outlined in the application form. The project will give input the health authorities on the possibility to use shared care on a larger scale to improve collaboration among primary and mental health care.

The results of WP1 will be used in WP2 to define and plan the shared care teams and their way of working. This model will then also be discussed with the GPs and other services as a part of WP2.

Plan of progress. Plan of progress is detailed in the application form.

2.4.Budget. The budget with comments is included in the application form.

3.Key perspectives and compliance with strategic documents

3.1.Compliance with strategic documents

The South-Eastern Regional Health Authority and Ahus have collaboration with primary care as a central goal in their strategic documents. The project is addressing several of the key challenges in specifying and implementing the national Collaboration Reform agreed in the Parliament.

3.2.Relevance and benefit to society

The model of shared care between primary care and mental health care may help develop better services for people with mental illness and co-morbid illnesses. Results and experiences with the model may also be generalizable to other aspects of the Collaboration Reform in Norway.

3.3.Environmental impact

The project is not expected to influence the physical environment, but can contribute to the improvement of the psycho-social environment for people with severe mental illness.

3.4.Ethical perspectives

Application of approval of the study is sent in February 2014 to the Regional Committee for Ethics in Research (REK), as well as to the Privacy Ombudsman at Akershus University Hospital. The goal of this project is to contribute to the improvement of services for people with mental illnesses, which has positive ethical aspects. Data collection can be experienced by some users as a burden, and perhaps positively by others.

3.5.Gender issues (Recruitment of women, gender balance, gender perspectives)

Both women and men will be recruited for participation in the study. Statistical analyses will include whether shared care changes how men and women are reached by the services, and whether there are differences in how men and women experience current practice and shared care.

4.Dissemination and communication of results

4.1.Dissemination plan The dissemination plan is written in the application.

4.2.Communication with users

The National Centre for User Experiences in Mental Health (Erfaringskompetanse.no) is an important collaborating partner designing the study, interpreting results, disseminating user experience and other results, and influencing health authorities and services to larger scale implementation of new successful models for service delivery. The results will be shared by users and to users in collaboration with these, including on their website www.erfaringskompetanse.no.

References

Ayazi T, Bøgwald K-P. Innvanderes bruk av poliklinisk psykiatrisk tjeneste. *Tidsskr Nor Legeforen* 2008; 128: 162- 5.

Craven, M., & Bland, R. (2006). Better practices in collaborative mental health care: An analysis of the evidence base. *Canadian Journal of Psychiatry*, 51(Suppl. 1), 7S-72S. Retrieved July 23, 2010, from http://www.ccmhi.ca/en/products/documents/04_BestPractices_EN.pdf.

Fleury MJ, Bamvita JM, Farand L, Aube D, Fournier L, Lesage A (2012a). GP group profiles and involvement in mental health care. *J Eval Clin Pract* 18(2):396-403

